
2. The central study coordinator will perform off-site eligibility screening of patients across all sites. Responsibilities of the central coordinator may include: 1) Notifying on-site coordinators of upcoming clinic visits of eligible or already enrolled patients 2) Contacting potentially eligible patients to give them information about the study prior to their clinic visit and discussion with an on-site coordinator 3) Contact eligible patients that were missed by on-site coordinators for virtual recruitment and consent 4) Make clinic visits for in -person patient recruitment and consent should onsite coordinators be unable to do so.

When an eligible patient is identified during a clinic visit, they will be approached by a study coordinator who will thoroughly explain the study, provide informational pamphlets, answer any questions, and ensure patient understanding of the study, each device, and their expectations. All study coordinators will have study tablets on which they can access our study website containing an entirely electronic patient enrollment platform, including baseline assessments and consent forms. Interested patients will be given this tablet and asked to review the information and study details and be given ample opportunity to ask any questions they may have. When ready, patients will be asked to read through and sign an e-consent document. Finally, they will be directed to create an account and profilee on our study website.

Eligible patients who have been missed during an in-clinic visit will be contacted by one of the study coordinators by phone. This may be via a phone call or, if unable to reach the patient, via text messaging and/or via e-email through a MyChart message. The following text messaging script will be sent to an eligible patient:

[figure not shown]
You have been selected by your Yale physician to participate in our Yale Heart Failure Digital Health Study. If eligible, you will be:

- compensated for your time
- getting access to new digital tools at no charge to you
- helping us make decisions on what types of tools to offer HF patients

We need your help! Please click on the following link to learn more:

https://yale.digitalhealthstudy.org/about-study

A study team member will be reaching out shortly to provide you with more information. If you have any questions, you can also respond to this text.

The following MyChart message will be sent:

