Any clinical data that is collected directly by the device, or any clinical information put into the device directly by the patient (e.g. a daily weight) will be accessible to the patient's physician via device-specific clinician dashboards available to the health care team. Importantly, we do not outline any standardized protocols for physicians to follow regarding use of this data. We will make it clear to all participating physicians that data collected from any device is purely informational and a supplement to regular clinical care. The collected data should not be used on its own to make any clinical decisions. Data must be used by providers in the context of all other clinical information available using their own clinical judgement. Further, the use of these devices should not disrupt usual clinic care in any way. Subjects will continue to see their provider as they would outside of the context of this study and will receive their usual care.

While physicians will have access to all clinical data collected via the devices, we have outlined a limited number of device-specific "triggers", such that when a key datapoint reaches a particular pre-specified threshold, the physician will be notified and asked to follow a standardized protocol in which the healthcare team calls the patient to check in and asks a series of standardized questions to assess the patient's condition and document the responses. We will not provide any pre-specified or standardized protocols beyond these "check-ins" and leave further care decisions up to the discretion and clinical judgement of the patient's

healthcare team. Any decisions made by the provider should be based on all clinical information available in addition to any data provided by a device. These triggers were selected based on the type of information collected by the device and the importance of these data points in the assessment of a CHF patient's status (as determined by our heart failure experts).

The three devices are described below, including the type of data collected and how it is stored, and which clinical data points will be used as triggers to notify the health care team.

Device Based Interventions:

- **BodyPort:** A novel data-driven smart scale that provides advanced cardiac monitoring and risk assessment data that feed directly to an analytics platform visible to providers. The scale also provides limited patient instruction and educational materials.

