7	/user_dashboard Returns data for populating Patient Dashboard	REST	JSC	DN		Yes (if PII is shared with Bodyport)	Bodyport Internal Use Only

Data to be used as triggers to notify providers when values reach specific thresholds may include the following, and are subject to change based on provider burden, utility, and frequency of alerts: weight, fluid index, heart rate, heart rate variability, impedance, electrocardiogram values, and systolic time intervals.

Coaching Based Interventions:

- **Noom:** A live, data-driven coaching application personalized to individuals for diet and weight management. Patients will be encouraged to use this application on a daily basis to track their activity and steps, their caloric intake, daily weights, blood pressure measurements, glucose measurements, and medication logs (i.e. patients can track when/if they take their daily medications). Educational modules and coaching support are also available through the application. While Noom does not have an information manual, they do have online support, FAQs, and instructions for individual portions of the application on their website: https://web.noom.com/support/. There are also several video tutorials that can be found here and will be given to the patient:
- Food Logging:
- iOS and Android : https://bit.ly/2D7Xanh
- Syncing Fitbit:
- iOS : https://bit.ly/2FtgRYn
- Android : https://bit.ly/2tfoomu
- Group Posts, Threads And Direct Messages (DM):
- iOS : https://bit.ly/2UOMoIK
- Android : https://bit.ly/2GxFSSH
- Meal Reminders:
- iOS : https://bit.ly/2VTmaGu
- Android : https://bit.ly/2SCEowR
- Syncing Apple Watch:
- iOS : https://bit.ly/2UpINB5
- Saving A Custom Dish:
- iOS : https://bit.ly/2H891pC
- -
- Patients will be given a thorough orientation to the application and these materials during enrollment.

The following data will be collected by Noom for use in our study and stored by Medullan in a HIPAAcompliant manner.

#	Source data	Data type	How Collected	Intended use	Collection Frequency	Data storage (specify where the data is stored and the compliance with HIPPA, ISO and or Hitrust)	Is it Protected Health Information (PHI)?	Additional Comments
1	Weight	Physical data	Both	Tracking/monitoring of weight, Calculation of caloric needs	Adhoc	Data is stored in the AWS cloud database. Noom is HIPAA compliant. AWS is SOC 1,2, &3 certified.	No	The patient (Noom user) can choose the data source - manual entry or connected device

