#	Source data	Data type	How Collected	Intended use	Collection Frequency	Data storage (specify where the data is stored and the compliance with HIPPA, ISO and or Hitrust)	Is it Protected Health Information (PHI)?
1	Biometrics readings	Medical and fitness device data	3rd-Party Connected Device	Experience personalization	Adhoc	HIPAA compliant	No
2	EHR / Clinical	Patient clinical history		Experience personalization	Adhoc	HIPAA compliant	Yes
3	EHR / Medications	Patient medications history		Experience personalization	Adhoc	HIPAA compliant	Yes
4	EHR / Preferences	Patient communication preferences		Experience personalization / communication	Adhoc	HIPAA compliant	Yes

5	EHR / Care team	Patient care team (provider relationship)	Experience personalization	Adhoc	HIPAA compliant	Yes
#	API description	API Type (SOAP (Simple Object Access Protocol), RPC (Remote Procedure Call) and REST (Representational State Transfer)	Data currently exchanged via this API	Collection Frequency	Data storage (specify where the data is stored an compliance with HIPPA, ISO and or Hitrust)	d the Is it Protected Health Information (PHI)?
1	Patient	REST	Patient entity per FHIR		http://hl7.org/fhir/STU3/patient.html	Yes
2	Conversation	REST	Transactional service for conversation support			No
3	Encounter	REST	Encounter entity per FHIR		http://hl7.org/fhir/STU3/encounter.html	No
4	Questionnaire Response	REST	QuestionnaireResponse per FHIR		http://hl7.org/fhir/STU3/questionnaireresponse.html	No

Patients will be thoroughly trained and oriented to their designated digital health product during their clinical visit by a study coordinator using on-site demo products (or over the phone if not consented in the clinic), and they will receive their product via mail. Each vendor will be responsible for the delivery, tracking, and distribution of their specific product.

Patients will be asked to actively engage with their product throughout the course of the study. If necessary, based on an eligibility questionnaire which assesses smart phone and data plan availability, patients will also be given a smart phone device that can be used with the product, such that no eligible patient is excluded on the basis of lack of access to a smart phone or internet connection.

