Patients randomized to the control arm of the study will receive usual care only. Patients in the control group will attend their normal clinic visits throughout the first three months of the study as they normally would, however, they will not receive any of the four digital health technologies above and their healthcare team will receive no additional information from any of these products.

Patient Follow-Up and Data Collection

All subjects will be enrolled in the study for a period of 6 months. The first three months will involve active clinic management, and subjects will be seen every 2-3 weeks as clinically indicated for an in-person visit as they normally would outside the research paradigm. Between visits, data regarding device usage, withdrawal rates, and device-generated health data described above will be passively collected from patients in the intervention arms of the trial and stored on a secure HIPAA-compliant database created by Medullan. During clinic visits, patients will also have the opportunity to meet with a study coordinator, who will administer surveys assessing device usability and user satisfaction (for those patients in the intervention groups only), as well as the KCCQ, health literacy and technology questionnaires, and medication adherence surveys (for all patients in the study, regardless of randomization status) to assess changes from baseline.

Once patients have "graduated" from the clinic, they will be followed for the final three months of the study via monthly phone calls from the study team. During this time, passive data collection from devices will continue. At 6 months, subjects will be asked to complete the final surveys appropriate to their randomization group either electronically or via telephone with one of our study coordinators.

Overview and Timeline of the Patient Experience

Day 0

- Patients who have passed initial screening will be approached by site study coordinators at a clinic visit (or via phone call/text messaging) regarding their interest in study participation.
- Study coordinators will describe, in detail, the study protocol with all interested patients, and patients will be asked to provide e-consent via a hippa-compliant, secure website set up for the purpose of the study, after all questions have been adequately answered.
- Consented patients will be asked to fill out a series of surveys and questionnaires used to collect baseline data for the study, including:

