- 6. Incarceration
- 7. Pregnancy
- 8. Currently homeless or residing in an unstable living situation (i.e., transitional housing, rehab facility, etc.)
- 9. Inability to consent
- 10. Currently enrolled in a study investigating a digital health product or technology
- 11. Life expectancy of less than 6 months as determined by the clinical judgement of the patient's primary physician
- 12. Weight greater than 400 pounds

- 13. Unable to stand up straight for thirty seconds without assistance, such as from a cane or walker
- 14. Non -english speaking

Note regarding pacemakers, and other implantable electronic devices:

While Bodyport has statements in their user manuals that their products are not to be used in patients with pacemakers and other electronic implanted devices, we have received statement from the vendor that the device is safe to use in this patient population.

Bodyport has stated that "With respect to the Bodyport product, there are no known safety issues related to the use of the device with patients with pacemakers or ICDs. However, we have not specifically tested the device in this population, and cannot make claims about its performance in these patients." We have included in the application an informational sheet on the theory of operation behind the Bodyport scale, which outlines the possible affect that a pacemaker or other device may have on the ability of the scale to perform accurate ECG readings, which is the reason that the warning statement regarding use in this patient population was included in the manual.

The BodyPort scale has been previously used in studies that do not exclude patients with pacemakers. Given that there are no safety concerns regarding the use of this device, we plan to enroll patients with pacemakers and other implantable devices, as excluding this population would be highly restrictive to the study.

9. How will **eligibility** be determined, and by whom?

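### Exclusion 10 does not cover private use of a tested product, so existing Noom users can dilute the Noom-versus-control contrast by an amount no described instrument would measure.

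*Combined protocol and SAP*

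**What the plan says.** Section I, item 8 lists 4 inclusion and 14 exclusion criteria. Exclusion 10 is the only one about digital products: "Currently enrolled in a study investigating a digital health product or technology". It depends on enrolment in a study, and no criterion mentions personal use.

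Section I, item 4 (Research Plan) describes the arms as follows.

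- **Control.** "Patients randomized to the control arm of the study will receive usual care only". On supply, the plan says of these patients that "they will not receive any of the four digital health technologies above". (The count of four conflicts with the three products named elsewhere, but this does not affect the point.) On the provider side, it says that "their healthcare team will receive no additional information from any of these products".
- **Product arms.** Data collected by or entered into the product "will be accessible to the patient's physician via device-specific clinician dashboards available to the health care team". Certain values trigger a notice to the physician and a standardized check-in call. A coordinator trains each patient on the product.
- **Noom.** It has no manual, but "they do have online support, FAQs, and instructions for individual portions of the application on their website", along with linked phone and watch tutorials.

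The only content given for the eligibility screen is that a phone is supplied "based on an eligibility questionnaire which assesses smart phone and data plan availability". The baseline instruments are the KCCQ, a medication adherence survey, and health and technology literacy surveys. At days 90 and 180 the usability survey, which covers frequency of use, goes to the intervention groups only. Usage outcomes come from the product databases.

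**The concern.** A patient who uses Noom privately and is in no other study can pass every criterion and be randomized to any arm. In the control arm nothing stops that patient from continuing. In the Noom arm the app itself is not new to that patient. Any benefit of the app so far is already in the baseline KCCQ, so change from baseline would show less of a product effect in such patients. The Noom-versus-control difference shrinks accordingly.

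At stake is how a weak or null Noom result could be read. Without a record of outside use, the investigators could not tell whether the product does little or whether part of the comparison was between users and users. Controls who take up an app after allocation raise the same difficulty, and randomization does not balance that uptake.

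**Working it through.** **1. Which products can be in private use.** Section II (Devices, item 2) says BodyPort lacks FDA clearance and describes Conversa as not approved. No private route to either is shown. Noom is also called not approved there, but its public support site and tutorials make private use a fair inference, though not a stated fact.

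**2. What an existing Noom user has in each arm.**

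| Component | Control | Noom arm |
|---|---|---|
| App (patient-facing) | already in use | already in use |
| Coordinator training | no | gained |
| Clinician dashboard | no | gained |
| Trigger check-ins | no | gained |

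The two arms therefore still differ for such a patient, but by less than the full intervention. In the BodyPort and Conversa arms the patient receives a new product, and background Noom use balances against control in expectation.

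**3. The plan's own sample size.** Inputs from Section I, item 13: difference 10 points, SD 11.8, power 90%, alpha 0.017 per comparison. Sidedness is not stated; two-sided is used because it matches.

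n per arm = 2 × (2.387 + 1.282)² × 11.8² / 10² = 37.5, rounded up to 38. A noncentral-t calculation gives 39, against 40 in the plan; a one-sided test would give 33. The stated figure reproduces.

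**4. Worst-case dilution.** Let a share f of patients in both arms be existing users with no further gain. The contrast becomes 10 × (1 − f). Power is Φ(contrast / SE − 2.387), with SE = 11.8 × √(2/50) = 2.36 at 50 per arm and 11.8 × √(2/40) = 2.64 at 40 per arm. The documents give no value for f, so the range is an assumption.

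| f | Contrast | n per arm for 90% | Power at 40 | Power at 50 |
|---|---|---|---|---|
| 0 | 10.0 | 38 | 92.0% | 96.8% |
| 5% | 9.5 | 42 | 88.8% | 94.9% |
| 10% | 9.0 | 47 | 84.7% | 92.3% |
| 15% | 8.5 | 52 | 79.8% | 88.8% |
| 20% | 8.0 | 59 | 74.1% | 84.2% |

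Example, f = 10% at 50 per arm: 9.0 / 2.36 − 2.387 = 1.43, and Φ(1.43) is about 92.3%. At the plan's final threshold of 0.016 the values at 50 per arm for 5%, 10% and 20% are 94.7%, 92.0% and 83.7%.

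The 40-per-arm column matters because the plan assigns the rise from 40 to 50 to uncertainty about the intraclass correlation, so it is not free margin for dilution. The check has no clustering term and takes 11.8 as the SD of the analysed change, as the plan's 40 implies.

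**5. Whether use would be seen.** Control patients have no product account in the study, are not given the usability survey, and complete no baseline survey described as asking about product use. Monthly calls between days 90 and 179 go to all arms and mention engagement with products, but define no data item on outside use.

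**The case against.** The strongest reply is that this is a pragmatic design. The comparator is usual care, product use is encouraged without a required schedule, and offering a product against background habits is a legitimate randomized contrast. Any distortion is conservative. Nothing shows that these heart failure patients use Noom, and even the worst-case formula leaves power at 50 per arm above 90% at 10% prior use. Exclusion 10 may also be an ordinary co-enrolment rule, since no rationale is given. All of this stands, and it limits the size of the point. It does not remove the gap: the stated purpose is efficacy against usual care, and outside use would be neither prevented nor counted.

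A reader might infer several stronger things that the documents do not support:

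- *An existing user in the Noom arm receives nothing new, or a self-using control is on the full intervention.* The dashboards, check-ins and training contradict the first. The statement that the control care team receives no product information contradicts the second.
- *All three comparisons are diluted by prior use.* Private use is plausible mainly for Noom, and the formula does not apply to the other two contrasts.
- *No question on use exists.* The eligibility questionnaire and technology survey are not reproduced. The documents show only that no such question is described.

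**Conclusion.** The gap is real but modest. Exclusion 10 admits private users of a tested product, realistically Noom users, and control-arm use is not a defined data item. The effect is dilution of the Noom-versus-control contrast toward no difference. It does not favour a product, and it does not make the plan's 40 or 50 per arm wrong.

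The size depends on an unknown share f. The dilution figures are an upper bound for prior use, because they assume no gain from the training, dashboard and check-ins. On that bound, power at 50 per arm stays above 90% at a 10% share and drops below it between 10% and 15%. Uptake by controls after randomization would add to the dilution and cannot be sized from the documents. The case for a change rests on how cheaply dilution can be reduced and measured, not on a demonstrated loss of power.

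**What to change.** 1. Extend exclusion 10 to patients currently using BodyPort, Noom or Conversa, and ask about this in the existing eligibility questionnaire before randomization. The look-back window is for the sponsor to set.
2. Add one item to the day-90 and day-180 surveys in all four arms on use of any of these products outside the assigned arm. Report it by arm, with a prespecified sensitivity analysis of the primary contrast.

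The cost is one changed criterion, one screening question and one survey item; surveys already go to every arm at both time points. The downside is that a few otherwise eligible patients are not enrolled. If the sponsor prefers to keep them, record current use at baseline and report the primary contrast with and without them.
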